### **8.3 Secondary End Points Analysis**

#### **8.3.1 Continuous Secondary End Point Analysis**

The continuous variables of initial claudication distance (ICD), measured at baseline, 3, 6, and 12 months will be analysed using a Multilevel Tobit model fitted to the censored ICD measurements. The Multilevel Tobit models will be performed to investigate the effect of the treatment indicator on the changes over time (3, 6, and 12 months), treating patient as a random effect, while the baseline measurement of the continuous ICD variable, treatment, time, interaction of time\*treatment, centre, group (SET vs non-SET), age, gender and BMI will be treated as covariates. Results of the Multilevel Tobit model will be presented (see Table 24 Section 8.9.6.1).

A summary table of proportion of patients who increased the ICD both by more than 60 and by more than 100 metres by treatment and by visit will be presented (Table 25 and Table 26)

The secondary end points concerned with quality of life scores (QoL) measured at baseline, 3, 6 and 12 months, will be analysed using separate ANCOVA models for each outcome variable. The measurements of quality of life are the Intermittent Claudication Questionnaire (ICQ), EuroQoL 5D 5L (EQ-5D-5L) and the SF-36.

The ANCOVA models of each of the QoL scores will be performed to investigate changes in QoL over time and to assess the difference between the two treatment groups, while controlling for the baseline measurement of the QoL score being analysed. Results of the ANCOVA models will be presented in tables (see Section 8.9.6.2).

All individual scores for ICQ, EuroQoL 5D 5L and the SF-36 will be presented as Plots. Plots of the mean QoL scores will be used to illustrate changes over time by treatment arm (Figure 1-3, Section 8.10).

Duplex ultrasonography (DU) measurements (Mean Volume Flow and Mean Time Average Mean Velocity) from the Haemodynamic assessment will be analysed using separate linear regression models. The linear regression models will be used to compare the Mean Volume Flow (VF) and Mean Time Average Mean Velocity (TAMV)

Imperial Clinical Trials Unit	STATISTICAL ANALYSIS PLAN	NESIC
-------------------------------	---------------------------	-------

for one leg (either the left or right) at 3 months, between the intervention group and the control group, using the baseline value of the specific measurement, the treatment indicator variable, centre, group (SET vs non-SET), age, gender and BMI as covariates. Results of these regression models will be presented in tables (see Section 8.9.6.3).

Laser Doppler Flowmetry (LDF), Duplex ultrasonography (DU) measurements, (Mean Volume Flow and Mean Time Average Mean Velocity) and Ankle Brachial Pressure Index (ABPI) for Left and Right Ankle from the Haemodynamic assessment will be analysed using separated Analysis of Covariance (ANCOVA) models.

Analysis of Covariance (ANCOVA) models for the Haemodynamic assessment for both Laser Doppler Flowmetry (LDF) and Ankle Brachial Pressure Index (ABPI) will be analysed, on treatment group indicator, controlling for the baseline measurement of the outcome assessment being analysed. They will be used to explore changes over time and assess the difference between the two treatment groups. Result of these ANCOVA models will be presented in tables (see Section 8.9.6.3).

The information collected with regards to compliance will be summarized by treatment. The information will be displayed in 3 different tables, one for each intervention: Exercise Advice (EA) compliance, Supervised Exercise Treatment (SET) compliance and the Neuromuscular Electrical Stimulation device (NMES) compliance. (Section 8.9.6.4).

### **8.3.2 Categorical End Point Analysis**

The device experience questionnaire for people who used the device will be summarized using descriptive statistics by treatment.

For the compliance classification a table of proportion of compliance by treatment will be presented.

### **8.4 Subgroup Analysis**

The subgroups are described in section 6.3. Summary statistics for the subgroups are presented (Section 8.9.7.1 and Section 8.9.7.2).

Subgroup analysis will investigate the effect of the intervention among subgroups. The subgroup effects will be based on the interaction between subgroup and treatment through a set of Tobit regression models. Tobit Regression will be used to evaluate the difference in absolute walking distance at 3 months between treatment groups. The Tobit model will include the AWD baseline measurement, a treatment indicator, a centre indicator and a group indicator (SET vs non-SET) as covariates . The results of the Tobit regression model will be reported (see Section 8.9.7.3).

In addition, as secondary analysis we will estimate both the difference between the proportion of patients whose absolute walking distance at 3 months improved by 60 metres or more from baseline and the difference between the proportion of patients whose absolute walking distance at 3 months improved by 100 metres or more from baseline using a chi-square test.

The secondary analysis will be repeated for each one of the subgroups.

All subgroup analyses will be presented in a Forest plot for comparison (see Figure 5).

### **8.5 Safety Analysis**

All safety variables will be summarized by treatment in the form of frequency tables for categorical variables or descriptive statistics for continuous variables. The tables will be produced using all randomized patients.

A list of all Protocol Deviations, Concomitant Medications, Adverse Events and Serious Adverse Events will be produced (see Section 8.9.8).

Imperial Clinical Trials Unit	STATISTICAL ANALYSIS PLAN	NESIC
-------------------------------	---------------------------	-------

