In the event that the participant is unable to attend in clinic or the site is unable to accommodate the on-site visit, this visit may take place remotely (i.e. over the telephone completely or in combination with postal questionnaires). This visit should only take place remotely if this has been previously discussed and agreed with the Trial Coordinating Centre. Missed assessments as a result of a remote visit should be re-scheduled at a later date as a separate on-site visit, where possible.

Sites should clearly document the mode of follow-up that takes place, such as face to face or over the [contact] Month Visit

Assessments and data collection will be collected as follows:

- **Treadmill test as per baseline**

Imperial Clinical Trials Unit	NESIC Clinical Study Protocol V6.0 24/03/2020	Form Number CR001A-T
-------------------------------	---	-------------------------

- **ABPI / Peripheral pulse as per baseline**
- **Drug history review**
- **Safety reporting**
- **Quality of Life questionnaires as per baseline**
- **Haemodynamic assessment**
  - **Laser Doppler flowmetry only (no duplex)**: this will be at rest for a 3minute duration in the most affected leg.
- **Compliance and resource diaries**
  - 4) **Exercise compliance** - Participants will be given a compliance diary to complete attendances at the SET if it runs past the 3-month visit (if SET centre), and record the type and frequency of exercise undertaken in their own time during the study period.
  - 5) **Resource diary** - Participants will be given a resource diary to complete health care resource use during the study period.

In the event that the participant is unable to attend in clinic or the site is unable to accommodate the on-site visit, this visit may take place remotely (i.e. over the telephone completely or in combination with postal questionnaires). This visit should only take place remotely if this has been previously discussed and agreed with the Trial Coordinating Centre. Missed assessments as a result of a remote visit should be re-scheduled at a later date as a separate on-site visit, where possible.

Sites should clearly document the mode of follow-up that takes place, such as face to face or over the telephone.

The 12-month follow up appointment will mark the end of the study participation.

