### **7.3 Adverse Event Recording**

For the purposes of the study, all AEs will be followed up according to local practice until the event has stabilised or resolved, whichever the sooner is. It is essential that all AEs that occur during the course of the study are appropriately reported in order to ensure the participants continuing safety. Of particular importance is the assessment of any event for *causality* and *expectedness* in relation to the device.

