**Table 1 Summary of Treatment groups**

Type of centre	Treatment
SET Centre	Control 1: Best Medical Therapy (BMT) + Exercise Advise (EA) + Supervised Exercise Therapy (SET)
	Treatment 1: Best Medical Therapy (BMT) +Exercise Advise (EA) + Supervised Exercise Therapy (SET) + Neuromuscular electrical stimulation (NMES)
Non-SET Centre	Control 2: Best Medical Therapy (BMT) + Exercise Advise (EA)
	Treatment 2: Best Medical Therapy (BMT) + Exercise Advise (EA) + Neuromuscular electrical stimulation (NMES)

- Treatment duration: 3 months of device use
- Follow-Up duration: 12 months (follow-up visits at 3, 6, and 12 months).

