### 8.9.8 Safety Analysis

**Table 82 Summary of Adverse Events by treatment**

Variable	Treatment  : NMES + EA and NMES+EA+SET	Control  : EA and EA+SET	Total N=(XX)
	N=(XX)	N=(XX)	
Severity			
Mild	XX (XX.X%)	XX (XX.X%)	XX (XX.X%)
Moderate	XX (XX.X%)	XX (XX.X%)	XX (XX.X%)
Severe	XX (XX.X%)	XX (XX.X%)	XX (XX.X%)
Life threatening or disabling	XX (XX.X%)	XX (XX.X%)	XX (XX.X%)
Fatal	XX (XX.X%)	XX (XX.X%)	XX (XX.X%)
Relationship Study device			
Definitely	XX (XX.X%)	XX (XX.X%)	XX (XX.X%)
Probably	XX (XX.X%)	XX (XX.X%)	XX (XX.X%)
Possibly	XX (XX.X%)	XX (XX.X%)	XX (XX.X%)
Unlikely	XX (XX.X%)	XX (XX.X%)	XX (XX.X%)
Not related	XX (XX.X%)	XX (XX.X%)	XX (XX.X%)
Not assessable	XX (XX.X%)	XX (XX.X%)	XX (XX.X%)
Site name			
Cambridge University Hospital	XX (XX.X%)	XX (XX.X%)	XX (XX.X%)
Dorset County Hospital	XX (XX.X%)	XX (XX.X%)	XX (XX.X%)
Hull and East Yorkshire Hospitals	XX (XX.X%)	XX (XX.X%)	XX (XX.X%)
Imperial College Healthcare	XX (XX.X%)	XX (XX.X%)	XX (XX.X%)
Newcastle Upon Tyne Hospitals	XX (XX.X%)	XX (XX.X%)	XX (XX.X%)
North Bristol	XX (XX.X%)	XX (XX.X%)	XX (XX.X%)
Nottingham University Hospitals	XX (XX.X%)	XX (XX.X%)	XX (XX.X%)
Royal Bournemouth & Christchurch Hospital	XX (XX.X%)	XX (XX.X%)	XX (XX.X%)
St George's University Hospitals	XX (XX.X%)	XX (XX.X%)	XX (XX.X%)
Taunton & Somerset	XX (XX.X%)	XX (XX.X%)	XX (XX.X%)
University Hospital Southampton	XX (XX.X%)	XX (XX.X%)	XX (XX.X%)

 Treatment: NMES + Local Available Exercise Therapy (NMES+EA and NMES+EA+SET)

 Control: Local Available Exercise Therapy (EA and EA+SET)

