**Table 84 List of all Adverse Events**

Subject id	Site Name	Adverse Description	Event	Frequency	Severity	Relationship device	Study	Treatment of Event	Outcome	SAE Classification	Reason	Treatment

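### The safety tables set no time window, so as written they combine 3 months of planned device use with 9 months after it and weaken the relative comparison between arms

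*SAP*

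**What the plan says.** The two periods are stated under Table 1 of SAP 5.3: "Treatment duration: 3 months of device use" and "Follow-Up duration: 12 months (follow-up visits at 3, 6, and 12 months". Protocol 5.6 adds that "The 12-month follow up appointment will mark the end of the study participation". Safety collection covers the whole of that time. Protocol 7.3 says "It is essential that all AEs that occur during the course of the study are appropriately reported", and the visit schedules (Protocol 5.7, SAP 5.8.1) mark safety reporting in the treatment phase and at months 3, 6 and 12.

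On analysis, SAP 8.5 says "All safety variables will be summarized by treatment in the form of frequency tables for categorical variables or descriptive statistics for continuous variables" and "The tables will be produced using all randomized patients". It names no time window. The variables that SAP 7.5 lists for analysis (for example severity, relationship to the device, outcome and site) include no date or period.

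The table shells in SAP 8.9.8 follow the same pattern:
- Table 82 ("Summary of Adverse Events by treatment") breaks events down by severity, relationship to the device and site. Table 83 does the same for serious events and adds outcome. Neither has a period.
- Table 84 ("List of all Adverse Events") shows no onset or stop date, and Table 85 copies its layout. By contrast, the protocol deviation listing (Table 4) has both a start and an end date.

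**The concern.** An effect of the device on adverse events is most likely to show while the device is in use. That is the first quarter of follow-up by plan. If one percentage per arm covers all 12 months, three quarters of the time at risk in both arms comes from a period when no device use is planned. Background events from those nine months enter both columns and make the arms look more alike in relative terms.

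The listings do not make up for this. Without dates, a reader of the planned outputs cannot reconstruct the device period. Nor can a reader check the relationship column, although Protocol 7.5 defines its Unlikely and Possible categories partly by the timing of the event relative to treatment.

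The cells of Tables 82 and 83 are also ambiguous. The column N is all randomised patients, but the shells do not say whether the entries count patients or events, and the two give different percentages.

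What is at stake is a clear randomised comparison of safety during device use. It matters because Protocol 1.8 reports that only two of 27 earlier studies of electrical stimulation commented on adverse events at all.

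**Working it through.** **The plan's own figures.** The documents give no figure for safety. The only input needed from the sample size is 96 per arm (SAP 5.7). It reproduces: a two-sample t test for 60 m with SD 120 m, two-sided 5% and 90% power, needs 86 per arm (172 in total, power 0.903), and 172/0.9 = 191.1, rounded up to 192.

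**Share of time on device.** 3/12 = 25% by plan, leaving 75% after it.

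**Rate ratio.** Assume a constant background rate, a device rate ratio of k in months 0-3, and no excess afterwards. The 12-month ratio is then (3k + 9)/12, so the relative excess (k - 1) is cut to a quarter.

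| k in months 0-3 | Ratio over 12 months |
|---|---|
| 1.5 | 1.125 |
| 2 | 1.25 |
| 3 | 1.50 |
| 4 | 1.75 |

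**Event counts.** Assume 96 per arm, 1 event per patient-year and k = 2.
- Months 0-3: control 96 x 1 x 0.25 = 24, device 48. Excess 24.
- Months 0-12: control 96, device 96 + 24 = 120. Excess 24.

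The excess is the same; the background against which it is read is four times larger. As a yardstick for precision only, the difference divided by the square root of the sum is 24/√72 = 2.83 for months 0-3 and 24/√216 = 1.63 for 12 months. At 0.5 events per patient-year the figures are 12/√36 = 2.0 and 12/√108 = 1.15.

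**Patients with at least one event.** Let b be the background risk per 3 months and e the independent risk that the device adds in months 0-3. The risk difference is (1 - b)e for months 0-3 and (1 - b)^4 e for 12 months, so it shrinks by the factor (1 - b)^3. For b = 10% and e = 15%:
- Months 0-3: 1 - 0.90 x 0.85 = 23.5% against 10.0%. Difference 13.5 points, risk ratio 2.35.
- Months 0-12: 1 - 0.90^4 x 0.85 = 44.2% against 34.4%. Difference 9.8 points, risk ratio 1.29.

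The standard error of the difference, with 96 per arm, is √[(0.10 x 0.90 + 0.235 x 0.765)/96] = 5.3 points for months 0-3. For 12 months it is √[(0.344 x 0.656 + 0.442 x 0.558)/96] = 7.0 points. The difference is smaller and less precisely estimated.

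**Range.** With b from 5% to 20% and e from 10% to 20%, the difference goes from 19.0 to 16.3 points in the most favourable case (b = 5%, e = 20%). It goes from 8.0 to 4.1 points in the least favourable (b = 20%, e = 10%). Nominal power of a two-sided 5% comparison of proportions, again only as a yardstick, is 25-97% for months 0-3 and 8-73% for 12 months.

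**The case against.** The strongest reply is that the plan already has a way to pick out device-related events. SAP 7.5 makes relationship to the device an analysed variable, and Tables 82 and 83 show it by arm from definitely to not related. An event judged to be related stays visible in its row however long follow-up lasts. This stands as partial mitigation. It is still a judgement made by staff who know the allocation (SAP 5.6), and controls have no study device to which an event could be attributed. It does not replace a comparison of all events between arms.

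Second, safety is descriptive. No between-arm test is planned, so no planned test loses power. That also stands, and the z and power values above only indicate precision. But the percentages and ratios that a reader takes from the tables are affected in the same way.

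Third, planned use is not actual use. The device questionnaire (SAP 7.4) asks about use beyond 3 months, and effects could be delayed. Either would reduce the dilution, and a fixed cut at month 3 would misplace some events. This is a reason to keep the 12-month total and to list dates.

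A reader might go further and infer that the trial could not show harm from the device. The documents do not support that: the excess count is preserved, related events have their own rows, and the data monitoring committee reviews safety during the trial (Protocol 11.4, SAP 9). A reader might also infer that onset dates are not collected. Only the planned outputs lack them; the documents do not show what the case report form holds. The column headings of Table 84 are partly run together in the text available, but SAP 7.5 lists no date either.

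**Conclusion.** The point holds as a shortcoming of the planned safety outputs. The tables have no time window and the listings show no dates, while planned device use covers a quarter of the collection period. That the tables combine all 12 months is the natural reading of SAP 8.5 alongside the visit schedule, but it is an inference. If another window was meant, the SAP should state it.

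Its size: under a constant background rate and no carry-over, the relative excess falls to one quarter, so a doubling appears as 1.25. The number of excess events does not change. For patients with at least one event, the difference falls from 13.5 to 9.8 points in the central example. All background rates and device effects here are assumed, because the documents give none. At the low end of the assumed range, even a table for months 0-3 would show little. The primary analysis is not affected. This is an inexpensive improvement to reporting, worth making because it gives a sharper randomised comparison during device use.

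**What to change.** In SAP 8.5, state the reporting windows. Split Tables 82 and 83 into months 0-3 (planned device period) and months 3-12, and keep the 12-month total. In each window give the number of patients with at least one event and, separately, the number of events, by arm and with all randomised patients as the denominator. Keep the relationship-to-device rows. Add onset and stop dates to Tables 84 and 85, so that events can also be read against any device use beyond month 3.

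The cost is a few extra columns and smaller counts per cell. Trial conduct does not change, and no new data are needed if onset dates are already recorded. If they are not, the visit at which the event was reported would give an approximate split.

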## 8.6 Missing Data

Before starting the data analysis, the level and pattern of the missing data in the baseline variables and outcomes will be established by forming appropriate tables. The likely causes of any missingness will be summarised.

### 8.6.1 Missing AWD Data

A summary table containing the reasons for missing primary outcome data and the relationship to the treatment will be presented.

Missing data are expected for some patients at the follow up visits at 3, 6 and 12 months as trial related patient assessment was suspended following NIHR guidance to individual trusts in response to the COVID-19 pandemic. For this reason, the missing primary outcome data will be assumed to be missing at random and multiple imputation will be used. If, when the missing data are analysed, they present another pattern other than missing at random, we will explore other methods of imputation.

This will be done only if more than 5% of the primary end point data are missing.

A sensitivity analysis on the primary endpoint, comparing both complete cases and imputed cases analysis, will be performed to assess the impact of any bias due to missing data. The estimated treatment effect and 95% confidence interval for each analysis will be presented, with the statistical significance summarised by the corresponding p-value.

### 8.6.2 Missing Data for other secondary outcomes

Missing data for the secondary endpoints QoL (Intermittent Claudication Questionnaire (ICQ) [10], EuroQoL 5D 5L (EQ-5D-5L), and Short form 36 (SF-36)) and the Laser Doppler Flowmetry (LDF) will be imputed.

#### 8.6.2.1 Quality of Life (QoL)

Missing data are expected for some patients at the 3, 6 and 12 months follow up visits as trial related patient assessment was suspended following NIHR guidance to individual trusts in response to the COVID-19 pandemic. [11] For this reason, we will assume that the missing pattern of the data is missing at random and chained equations (a multiple imputation method for imputing the missing scores) will be used. When the missing data are analysed, if they present another pattern other than missing at random, we will explore other methods of imputation.

#### 8.6.2.2 Laser Doppler Flowmetry (LDF)

Multiple imputation, under the ‘missing at random’ assumption, will be undertaken for all participants who have missing values in the Laser Doppler Flowmetry outcome. If when the missing data is analysed and it presents another pattern other than missing at random, we will explore other methods of imputation. This will be done only if 10% or more of data is missing.

#### 8.6.2.3 Sensitivity of Secondary Outcomes Analysis to Missing Data

A sensitivity analysis on the secondary outcomes, both complete cases and imputed cases, will be performed to assess the impact of any bias due to missing data. The estimated treatment effect and 95% confidence interval for each analysis will be presented, with the statistical significance summarised by the corresponding p-value.

## 8.7 Interim Analysis

No formal interim analysis is planned for this trial.

Imperial Clinical Trials Unit	STATISTICAL ANALYSIS PLAN	NESIC
-------------------------------	---------------------------	-------

## 8.8 Sensitivity Analysis

We will carry out sensitivity analyses as detailed below.

### 8.8.1 Compliance

For the primary and secondary endpoints, we will assess the impact of compliance by performing a subgroup analysis on the compliers population using the compliance definition in section 8.9.6.4. The estimated treatment effect and 95% confidence interval for each analysis will be presented, with the statistical significance summarized by the corresponding p-value.

### 8.8.2 Sensitivity to Alternative Data collection (due to COVID-19)

Meyer [12] lists recommendations on how to address issues related to study objectives, inference, and statistical analysis for trials conducted during the COVID-19 Pandemic. From the assessment list suggested only missing data and the impact of alternative ways of collecting data are the factors that could have an impact on the NESIC trial. The missingness of data has been discussed already in section 8.6.

To protect the safety and wellbeing of patients, the NESIC trial submitted an amendment on the protocol to allow the follow up data to be done remotely (i.e., over the telephone completely or in combination with postal questionnaire) during the pandemic period. For issues of alternative methods of data collection, Meyer recommends performing a sensitivity analysis to judge whether these alternative ways to collect data are exchangeable.

To assess whether this alternative way to collect follow up data has had an impact on the trial a sensitivity analysis on the secondary outcome of QoL will be performed, comparing all cases and cases where the data that were collected in other ways than originally stipulated in the Protocol have been removed. The estimated treatment effect and 95% confidence interval for each analysis will be presented, with the statistical significance summarised by the corresponding p-value.

Imperial Clinical Trials Unit	STATISTICAL ANALYSIS PLAN	NESIC
-------------------------------	---------------------------	-------

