## 5.6 Follow-up

Follow-up data will be collected at 3 months, 6 months and 12 months. These visits should be performed at the study site to allow the treadmill test, ABPI / Peripheral

C001A-T v4.0 Effective 5th April 2017

Imperial Clinical Trials Unit	NESIC Clinical Study Protocol V6.0 24/03/2020	Form Number CR001A-T
-------------------------------	---	-------------------------

pulse, haemodynamic assessments to take place, however, in the event that the participant is unable to attend in clinic or the site is unable to accommodate the on-site visit these visits may take place remotely (i.e. over the telephone completely or in combination with postal questionnaires). These visits should only take place remotely if this has been previously discussed and agreed with the Trial Coordinating Centre. Missed assessments as a result of a remote visit should be re-scheduled at a later date as a separate on-site visit, where possible.

Sites should clearly document the mode of follow-up that takes place, such as face to face or over the [contact] Month Visit (end of treatment phase)**

Assessments and data collection will be collected as follows:

- **Treadmill test as per baseline**
- **ABPI / Peripheral pulse as per baseline**
- **Drug history review**
- **Safety reporting**
- **Quality of Life questionnaires as per baseline**
- **Haemodynamic assessment as per baseline**
  - **Duplex ultrasonography:**
    - **In the control group:** only resting values will be undertaken over a 3-minute period.
    - **The intervention group** will have these parameters measured at rest, at 15 and 30-minutes into device use and then at 1 and 5 minutes after device cessation.
  - **Laser Doppler flowmetry:**
    - **In the control group:** this will be at rest for a 3 -minute duration
    - **The intervention group:** data will be collected at rest until 5 minutes after device cessation.
- **Compliance and resource diaries**

Imperial Clinical Trials Unit	NESIC Clinical Study Protocol V6.0 24/03/2020	Form Number CR001A-T
-------------------------------	---	-------------------------

- 1) Exercise compliance** - Participants will be given a compliance diary to complete attendances at the SET (if SET centre), and record the type and frequency of exercise undertaken in their own time during the study period.
- 2) Resource diary** - Participants will be given a resource diary to complete health care resource use during the study period.

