## 5.8 Schedule of Time and Events

The actual study commenced recruitment on 21st March 2018 and was expected to recruit for 15 months but was extended to finish on 31st March 2020 (granted by REC/HRA). However recruitment was temporarily paused on 20th March 2020 due to COVID-19. The last follow up will end one year after the recruitment of the last patient. The summary table of Visit Schedule and the summary of Treatment time are displayed in Section 5.8.1 and Section 5.8.2 respectively.

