### 8.2 Primary End Point Analysis

The primary endpoint is the absolute walking distance (AWD) measured by treadmill test at 3 months.

The measured absolute walking distance, by treatment group and time point, will be presented for all patients within the ITT population in a summary table (Table 16, Section 8.9.5).

The primary analysis will estimate the difference in the absolute walking distance at 3 months between the two treatment groups (NMES + local available exercise therapy vs. local available exercise therapy only) by using a

Tobit regression model to address the cut-off point of 15 min (where the distance reached to this point will be censored at 790 metres). The model will include the measurements of AWD baseline, treatment indicator, centre indicator and group indicator as covariates. The results of the Tobit regression model will be reported (see Table 17, Section 8.9.5).

As a secondary analysis of the primary endpoint, we will estimate the difference between the groups in the proportion of patients that increased the absolute walking distance at 3 months by 60 metres or more from baseline using a chi-square test (Table 18). This analysis will be repeated for the proportion of patients that increases the AWD at 3 months by 100 metres or more (Table 19).

A summary table of proportion of patients who increased the AWD both by more than 60 and by more than 100 metres by treatment and by visit will be presented (Table 20 and Table 21)

A Multilevel Tobit model will be used to investigate the difference in absolute walking distance between the two treatment groups at 3, 6 and 12 months adjusting for the following independent baseline covariates:

- AWD baseline measurement
- Treatment
- Time
- Time\*Treatment interaction,
- Centre
- Group (SET vs non-SET)
- Age
- Gender
- BMI
- Smoking Status

The results of the Multilevel Tobit model will be presented (Table 22, Section 8.9.5)

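### The share of visits due in the pandemic rises with visit number, but no over-time model has a calendar-period term, so change from 3 to 12 months partly reflects the pandemic

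*SAP*

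**What the plan says.** On timing, SAP 5.8 records: "The actual study commenced recruitment on 21st March 2018", and later that "recruitment was temporarily paused on 20 th March 2020 due to COVID-19". It adds: "The last follow up will end one year after the recruitment of the last patient". Visits are at 3, 6 and 12 months. Protocol V6.0, dated 24 March 2020, introduced remote follow-up: where attendance on site is not possible, "these visits may take place remotely (i.e. over the telephone completely or in combination with postal questionnaires"). This needs prior agreement from the coordinating centre, and missed assessments are to be rebooked on site where possible (Protocol 5.6). SAP 8.6.1 notes that trial assessments were suspended.

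On analysis over time:

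- **AWD.** SAP 8.2: "A Multilevel Tobit model will be used to investigate the difference in absolute walking distance between the two treatment groups" over the three follow-up visits. Table 22 lists baseline AWD, Treatment, Time, Treatment*Time, Centre, Group, age, gender, BMI and smoking.
- **ICD.** Table 24 has the same terms without smoking.
- **QoL.** SAP 8.3.1: "The ANCOVA models of each of the QoL scores will be performed to investigate changes in QoL over time", and to compare the arms. The listed terms are treatment and baseline only.
- **Laser Doppler flowmetry (LDF) and ankle brachial pressure index (ABPI).** SAP 8.3.1 gives the same two purposes and the same two terms.
- **Figures.** SAP 8.10 plans time-trend plots of the QoL scores.

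No model contains calendar period or visit mode. On the pandemic itself, SAP 8.8.2 says that "only missing data and the impact of alternative ways of collecting data are the factors that could have an impact on the NESIC trial". It plans one check beyond the missing-data work: QoL with and without data collected in a way other than the protocol first specified.

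**The concern.** Patients were enrolled over two years up to the start of the pandemic, and each was followed for a year. Later visits are therefore more likely to fall in the pandemic, whatever the accrual curve. Time since randomisation and the pandemic overlap, and a model with only a Time term cannot separate them.

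Restricted activity could change walking, exercise and QoL in both arms. It could also change the value of a home device relative to exercise advice. A common decline would then read as loss of benefit between 3 and 12 months. An effect that differed by arm would read as a treatment effect changing with time since randomisation. SAP 8.8.2 leaves out any real change in the outcome during the pandemic, and its one check concerns how QoL was collected, not when.

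**Working it through.** **Plan's own figures.** The documents give no share of pandemic-era visits and no count of remote visits, so there is no stated figure to reproduce. The planned total of 192 serves only to turn shares into counts. It reproduces: 86 per arm gives 90.3% power by the t-test for 60 m with SD 120 m, and 172/0.9 = 191.1, rounded up to 192.

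**Inputs.** Recruitment start 21 March 2018 and pause 20 March 2020 (SAP 5.8), 730 days apart. Visits at 3, 6 and 12 months (SAP Table 1). Assumptions: the era starts on 20 March 2020, recruitment did not resume, and accrual follows one of the shapes below.

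**Share of visits due in the era.** A visit at month m falls in the era if the patient was recruited on or after 20 March 2020 minus m months. Let f be the fraction of the 730 days before that cut-off. The share is 1 − f for uniform accrual, 1 − f² for a linear ramp-up and (1 − f)² for a linear tail-off.

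| Visit | Cut-off | f | Uniform | Of 192 | Ramp-up | Tail-off |
|---|---|---|---|---|---|---|
| 3 months | 20 Dec 2019 | 639/730 | 12.5% | 24 | 23.4% | 1.6% |
| 6 months | 20 Sep 2019 | 548/730 | 24.9% | 48 | 43.6% | 6.2% |
| 12 months | 20 Mar 2019 | 364/730 | 50.1% | 96 | 75.1% | 25.1% |

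Under uniform accrual, an era start of 1 March 2020 gives 15%, 28% and 53%; 24 March gives 12%, 24% and 50%. The share rises with visit number in every case.

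**Effect on the Time term.** Suppose the pandemic shifts the outcome by d in both arms, true change is zero and all visits are observed. Without an era term, the 12- versus 3-month coefficient has expectation d × (p12 − p3), where p is the share due in the era.

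- Uniform: 0.501 − 0.125 = 0.38 of d.
- Ramp-up: 0.751 − 0.234 = 0.52 of d.
- Tail-off: 0.251 − 0.016 = 0.24 of d.

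**Simulation** (192 patients, uniform accrual, linear model without censoring, all visits observed, true treatment effect 60 m, shift sizes assumed; Monte Carlo error about 1 m):

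| Shift, control / device | Time, 12 v 3 months, no era term | Same, era main effect added | Treatment*Time at 12 months, no era term | Same, era main effect added |
|---|---|---|---|---|
| −30 / −30 m | −12.1 m | −0.9 m | 0.2 m | 0.1 m |
| −60 / −60 m | −22.0 m | 0.3 m | −1.0 m | −0.9 m |
| −60 / −30 m | −23.5 m | −6.8 m | 12.3 m | 12.1 m |

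The formula gives 0.377 × 30 = 11.3 m and 0.377 × 60 = 22.6 m, in agreement. With a common shift, the 3-month treatment effect stays at about 60 m (59.7 and 60.6 m) with or without the era term.

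In the last row the arms differ by 30 m in the era. Treatment*Time then moves by about 0.377 × 30 = 11.3 m, and an era main effect alone does not remove it. In a separate simulation, a 0.3 SD difference in device effect during the era biased Treatment*Time by 0.11 SD. With era and era-by-treatment terms the bias was about zero.

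**The case against.** The strongest reply is that the trial's questions are comparative. SAP 8.2 describes the multilevel model as a comparison of the two arms. Arms were randomised concurrently within centre, so a common shift cancels at every visit. That stands, and it confines the concern to the Time coefficient, within-arm change and the meaning of Treatment*Time.

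The second reply also stands in part. Treadmill, ABPI and LDF measurements cannot be made by telephone or post, and assessments were suspended. Many pandemic-era values of these outcomes will be missing, not shifted, so the 0.38 is too large for them. QoL is the most exposed outcome, but its listed model has no time coefficient. Error rates for a test of change from 3 to 12 months therefore do not apply to any listed QoL test. The exposure there lies in the time-trend plots and in any description of change.

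A reader might infer four stronger points that the documents do not support:

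- **That half the 12-month visits were remote.** The percentages are visits due. Remote visits are a subset of unknown size.
- **That the QoL check in SAP 8.8.2 deletes the whole pandemic period.** On-site visits held in the period remain in the reduced data set. The check addresses mode but leaves period unexamined.
- **That comparing remote with in-person QoL would settle the matter.** That comparison is not randomised and depends on why patients could not attend.
- **That late recruits were almost all non-SET.** SAP 5.1 says three SET centres took non-SET patients after the SET sample was full, but gives no date and no split.

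**Conclusion.** The concern holds for change over follow-up. The rising share follows from the recruitment dates and visit schedule under any accrual shape. Its size does not: 12.5%, 25% and 50% assume uniform accrual, and linear shapes give about 2-23%, 6-44% and 25-75%.

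The 3-to-12-month Time coefficient absorbs about 0.38 of a common pandemic shift under uniform accrual with complete data (0.24 to 0.52 under the linear shapes), and less where on-site tests are missing. An assumed 30 m common shift would give roughly 11 to 12 m of apparent decline, about a fifth of the 60 m planned effect. The documents do not say whether any shift occurred.

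A reader might conclude that the primary result is biased. It is not biased by a common shift: the 3-month contrast and the between-arm contrast at each visit are unaffected. An arm-dependent shift changes what Treatment*Time means, and only a model with the era-by-treatment term can show it. This is an inexpensive improvement to secondary analyses that the SAP already intends to report.

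**What to change.** In SAP 8.8.2:

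1. Add a sensitivity analysis of the AWD, ICD and QoL over-time analyses with an era indicator and era*treatment. Define era from the scheduled date (randomisation date plus 3, 6 or 12 months), before versus on or after 20 March 2020, so that it cannot depend on treatment.
2. In the QoL model, specify visit explicitly; the current ANCOVA has no time term to adjust.
3. Report observed and remote counts by visit, era and arm.
4. Base any statement about change or loss of benefit between 3 and 12 months on these estimates.

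The change needs SAP wording and dates that follow from randomisation. It costs one or two degrees of freedom and widens the intervals for the time terms, most where few pandemic-era treadmill tests were observed. Two limits should be stated. A visit due just before the cut-off but held after it is classed as pre-pandemic. The era term also partly compares later with earlier recruits, so Centre and Group should stay in the AWD and ICD models and be added to the QoL sensitivity model.
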